## Design

Regular exercise is well known to have a positive effect on health [1,2]. Many of these benefits are associated with improving maximal oxygen uptake ( $\dot{V}O_{2max}$ ) [3,4]. Increasing  $\dot{V}O_{2max}$  through exercise training may improve cardiometabolic health, quality of life and increase life-expectancy [5,4].

Popular training methods aimed at improving  $\dot{V}O_{2max}$  are circuit and high intensity interval training (HIIT) and are routinely adopted by the general population, health and fitness professionals and researchers [6]. Circuit training (CT) is typically performed at a moderate or high intensity, over a period of 30-50 minutes and involves a range of aerobic, body weight and resistance exercises with minimal rest [7,8]. Low-volume HIIT is defined as 'brief, intermittent bursts of vigorous activity, interspersed by periods of rest or low intensity exercise' [9], typically prescribed at a training intensity between 80 and 100% of heart rate maximum ( $HR_{max}$ ) [10].

Whole-body CT and low volume HIIT consisting of eight to twelve one-minute interval bouts, interspersed with a similar recovery time have been shown to improve cardiometabolic health and cardiorespiratory fitness (CRF) [8,11-16]. Increases in  $\dot{V}O_{2max}$  and the anaerobic threshold (AT) have been observed following CT, however published studies are limited to sedentary and older populations, with further markers of CRF not fully explored [8,17]. Comparable improvements in  $\dot{V}O_{2max}$  and the AT have been shown following low volume HIIT, with increases in maximum oxygen pulse ( $\dot{V}O_2/HR$ ) also observed [16,18,19]. However, there is limited evidence directly comparing both training methods across a range of CRF markers, as such it is unknown which approach is most beneficial [20,21].

Direct comparisons have been made investigating low volume HIIT and moderate intensity continuous training (MICT), which is typically 30-60 minutes in duration adopting the same modality

of exercise [15,16,14]. The results demonstrate low volume HIIT to be a time efficient method, eliciting greater improvements in  $\dot{V}O_{2max}$ , although these findings are not consistently shown [22].

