While HIIT and CT are feasible and effective at improving CRF, no study has directly investigated the two. Therefore, the aim of this study was to compare the effect of two weekly sessions of low volume HIIT and CT over an eight-week period on  $\dot{V}O_{2max}$  in apparently healthy middle-aged adults. We also investigated changes in other markers of CRF such as the first ventilatory anaerobic threshold ( $\dot{V}O_2$  at VAT) and maximum  $\dot{V}O_2/HR$ .

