### **Study Design**

Participants were enrolled in a randomised control trial at the University of Hull to either eight weeks of HIIT or CT (two supervised sessions per week, accompanied by an exercise physiologist). A sample size of 38 using G\*Power 3.1 software was calculated based on previously published data in which the mean difference between HIIT and MICT was  $3.2 \text{ ml}\cdot\text{kg}^{-1}\cdot\text{min}^{-1}$  with a pooled standard deviation of  $3 \text{ ml}\cdot\text{kg}^{-1}\cdot\text{min}^{-1}$  [19]. Statistical significance was set at  $\alpha = 0.05$  and power set to 0.95. To allow for 10% attrition 42 individuals were recruited to the study. To assess the effectiveness of the interventions as determined by  $\dot{V}O_{2max}$ , a maximal cardiopulmonary exercise test (CPET) to volitional exhaustion on an electronically braked cycle ergometer at baseline (visit one), and following an eight-week exercise intervention of HIIT or CT (visit two) was conducted. When attending the assessments participants were asked not to take part in any strenuous exercise 24 hours prior to the appointment, to wear suitable comfortable clothing and avoid a large meal. Visit two CPET was performed within six days of completing the exercise interventions. A thorough warm-up and cool down before and after each exercise session. All were asked to maintain their habitual physical activity patterns during the intervention. Body mass index (BMI) was calculated by dividing body weight [23] by height in meters squared and was presented as  $\text{kg}\cdot\text{m}^{-2}$ . Resting blood pressure was measured after 15 minutes of rest using a sphygmomanometer (A.C. Cossor & Son Ltd, London UK)

and stethoscope (3M Healthcare, St Paul, MN). To provide a comprehensive account of the study the Consensus on Exercise Reporting Template (CERT) was consulted [24].

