### **Statistical Analysis**

Statistical analysis was conducted using SPSS version 24 (IBM, New York, USA). An independent t-test was used to identify group differences at baseline. Assumptions of normality were verified using the Shapiro-Wilk test. Skewness and kurtosis of distribution was visually examined. Non-normally

distributed data was presented as median and interquartile range (IQR). A two-way (condition x time) repeated measures analysis of variance (ANOVA) was used to compare CRF pre-and post-training. Post-hoc analysis for the main effects and interactions was assessed using a Bonferroni adjustment. Group differences were compared using independent t tests. Variables were displayed as mean with 95% confidence intervals (95% CI) or standard deviation ( $\pm$ ) where specified. Partial eta squared ( $\eta_p^2$ ) effect sizes were also calculated with 0.01, 0.06 and 0.14 representing small, medium and large effect sizes, respectively [35].

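### Does the plan need a committed 95% CI for the HIIT minus CT difference in change, in place of labelled partial eta squared?

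*Combined protocol and SAP*

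**What the plan says.** The Design section states that "the aim of this study was to compare the effect of two weekly sessions of low volume HIIT and CT over an eight-week period", with VO2max as the outcome. The motivation is that "as such it is unknown which approach is most beneficial". Other fitness markers are secondary: "We also investigated changes in other markers of CRF such as the first ventilatory anaerobic threshold".

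The Statistical Analysis section plans a condition-by-time repeated measures ANOVA with Bonferroni-adjusted post-hoc comparisons. It adds "Group differences were compared using independent t tests" and, on display, "Variables were displayed as mean with 95% confidence intervals (95% CI) or standard deviation" where specified. Partial eta squared comes last, as an addition: "effect sizes were also calculated with 0.01, 0.06 and 0.14 representing small, medium and large effect sizes, respectively".

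The interval sentence is about variables in general and allows an SD instead. It neither names nor excludes the between-group difference in change.

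**The concern.** A trial that asks which of two programmes is better should give the difference in ml/kg/min, with its sign and precision. The only effect-size measure the plan names is partial eta squared, which has neither sign nor units. The t test sentence names a test but no estimate, and does not say whether it applies to post-training values or to change. Separate intervals on each arm's mean at each visit do not give the interval for the difference in change, because that depends on the within-person correlation.

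The labels add to the unease. Eta squared cannot be negative, so it is above zero on average even when the programmes are equivalent. In a trial of about 40 people that average is above the cut for small. A reader who took the labels at face value could believe in a small or medium advantage where the data show none. The worst case would be a non-significant result presented as a medium effect.

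**Working it through.** **Inputs.** From Study Design: 38 required, SD 3 ml/kg/min, planning difference 3.2 ml/kg/min, and 42 recruited (38 × 1.10 = 41.8, rounded up). From Statistical Analysis: cut points 0.01, 0.06 and 0.14. Assumptions: 1:1 allocation (19 per arm at N = 38), complete pairs, and the SD of 3 applying to change, which the plan does not say. The plan gives no figure of its own on this point to reproduce.

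**1. Behaviour of the labels with no true interaction.** The interaction has 1 and N − 2 degrees of freedom, and eta squared = F/(F + df), so a cut c corresponds to F = df × c/(1 − c). The null mean of eta squared is 1/(N − 1).

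| | N = 38 (df 36) | N = 42 (df 40) |
|---|---|---|
| Null mean | 1/37 = 0.027 | 1/41 = 0.024 |
| P(small or larger) | P(F ≥ 0.364) = 55.0% | P(F ≥ 0.404) = 52.9% |
| P(medium or larger) | P(F ≥ 2.298) = 13.8% | P(F ≥ 2.553) = 11.8% |
| P(large) | P(F ≥ 5.860) = 2.1% | P(F ≥ 6.512) = 1.5% |
| Small only | 55.0 − 13.8 = 41.2% | 52.9 − 11.8 = 41.1% |
| Eta squared at p = 0.05 | 4.113/(4.113 + 36) = 0.103 | 4.085/(4.085 + 40) = 0.093 |
| Medium or larger, not significant | 13.8 − 5.0 = 8.8% | 11.8 − 5.0 = 6.8% |

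The null distribution is strongly skewed: its median at N = 38 is 0.0127, only just above the cut for small. Most of the 55% is therefore the label small. The type I error rate of the F test stays at 5%.

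**2. The interval is already in the planned analysis.** With two arms, two time points and complete pairs, the interaction F equals the square of the equal-variance t statistic comparing change scores. At N = 38:

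- SE = 3 × √(2/19) = 0.973
- critical t on 36 df = 2.028
- half-width = 2.028 × 0.973 = 1.97 ml/kg/min (1.32 if the SD of change is 2; 2.63 if it is 4)

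A result exactly at the medium cut has t = √2.298 = 1.516. The difference is 1.516 × 0.973 = 1.48, with 95% CI −0.50 to 3.45. The p-value is 0.138, so the planned test already says that the difference is not established.

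**3. What a reader can recover if the interval is not printed.** Half-width = critical t × |difference|/√F. Take an observed eta squared of 0.01, where the difference is √0.364 × 0.973 = 0.587 and p = 0.55.

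- From eta squared alone, rounded to two decimals (0.015 to 0.005): 1.61 to 2.80.
- From p rounded to two decimals (0.545 to 0.555): 1.95 to 2.00.
- From F rounded to two decimals: 1.97 to 2.00.

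These treat the difference as exact. If it is known only to within 0.05, the half-width moves by 0.05/0.587 = 8.5%, that is 1.81 to 2.14. The wide range appears only if rounded eta squared is the sole statistic printed.

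**The case for a change.** The strongest case for a change is that it costs almost nothing. One sentence would commit the report to the difference in change with its 95% CI, and the estimate comes from a test equivalent to the planned F. The text as it stands could be satisfied by SDs, p-values and labels alone. Back-calculation should not be left to the reader, and it breaks down as the observed difference approaches zero, because a rounded difference then carries little information.

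Much of this stands as reporting advice. The interval is the most useful single result the trial can give, and it is not expressly promised. The label frequencies are also right.

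The step from there to a defect does not stand. The argument treats eta squared as the plan's summary of the comparison, whereas it accompanies means with intervals or SDs and a test of the group difference. It also presupposes that the labels will be read as evidence, and the plan does not use them that way. Nor does the general sentence on intervals rule out showing change, or the difference in change, with a 95% CI. The results tables are not part of these documents, so omission cannot be inferred. Removing a conventional set of labels is a matter of taste.

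**Conclusion.** No change to the plan is needed. The missing sentence is a gap that an analyst fills sensibly from output the planned analysis already produces. If the plan is followed as written, the estimate, the test, the p-value and the conclusion about HIIT against CT are the same with or without it.

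The effect is on description only. Under no true interaction, 8.8% of trials at N = 38 (6.8% at N = 42) would carry a label of medium or larger beside a non-significant test. The loss of precision from an unprinted interval is small provided that p or F is reported numerically, which is ordinary practice but not stated in the plan. The 1.97 ml/kg/min half-width rests on 19 completers per arm and on the SD of 3 describing change.

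When the results are written up, the difference in change with its 95% CI is worth giving for VO2max, VO2 at VAT and maximum VO2/HR, and the eta squared labels should not be read as evidence of an effect. That is a reporting courtesy, not a correction.
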